6.3 Excluded Concomitant Medications and Procedures

The following medications and procedures are prohibited during the study:

Bleomycin: The concomitant use of brentuximab vedotin and bleomycin has resulted in increased pulmonary toxicity versus bleomycin alone. Co-administration of brentuximab vedotin and bleomycin is a contraindication.

Use of the following medications and procedures should be considered with caution:

Interaction with medicinal products metabolized through CYP3A4 route:

CYP3A4 Inhibitors: Co-administration of brentuximab vedotin with ketoconazole, a strong CYP3A4/P-gp inhibitor, increased the exposure to the antimicrotubule agent MMAE by approximately 73%, and did not alter the plasma exposure to brentuximab vedotin. Therefore, co-administration of brentuximab vedotin with strong CYP3A4 and P-gp inhibitors may increase the incidence of neutropenia. If neutropenia develops, refer to Table 6-1 Recommended brentuximab vedotin Dose Modifications for Treatment Associated Toxicity Excluding Neuropathy

CYP3A4 Inducers: Co-administration of brentuximab vedotin with rifampicin, a strong CYP3A4/P-gp inhibitor inducer, did not alter the plasma exposure to brentuximab vedotin; however it reduced exposure to MMAE by approximately 31

CYP3A4 Substrates: Co-administration of midazolam, a CYP3A4 substrate, with brentuximab vedotin did not alter the metabolism of midazolam; therefore brentuximab vedotin is not expected to alter the exposure to medicines that are metabolized by CYP3A4 enzymes.

6.4 Permitted Concomitant Medications and Procedures

The following medications and procedures are allowed during the study:

- The use of topical, inhalational and ophthalmic steroids is permitted. Corticosteroids are permitted as part of a chemotherapy premedication regimen or for the treatment of study disease per institutional standards.
- The use of platelet and/or red blood cell supportive growth factors or transfusions when applicable is allowed.
- The use of colony stimulating factors for the treatment of neutropenia per institutional practice is permitted during therapy.

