1.5 Study Rationale and Selection of Study Drug Doses

Although anthracycline-based regimen such as CHOP (cyclophosphamide, doxorubicin, vincristine, and prednisolone) has been the standard treatment of aggressive non-Hodgkin's lymphomas,¹⁰ patients with EBV-positive lymphomas might relapse more frequently than those with EBV-negative lymphomas. Because CD30 is frequently expressed in EBV-infected lymphoid cells,¹¹ it is a druggable target at EBV- and CD30-positive lymphomas. In addition, CD30 is overexpressed in EBV-positive lymphomas: extranodal NK/T-cell lymphoma, nasal type, 72%¹²; EBV-positive peripheral T-cell lymphoma, 43%¹³; and EBV-positive diffuse large B-cell lymphoma (DLBCL) of the elderly, 70%.¹⁴

The high CR rate and ORR obtained with brentuximab vedotin in 2 single-arm phase 2 studies in relapsed or refractory HL (SG035-0003) and relapsed or refractory sALCL(SG035-0004) suggest that single-agent brentuximab vedotin may be active against CD30-positive lymphomas other than HL and sALCL. Single-agent brentuximab vedotin showed antitumor activity against refractory B-cell lymphomas with variable CD30 expression (0-100%): ORR 40% (CR 16%) and median duration of response 36 weeks (range, 0.1-62.3 weeks) for DLBCL; and ORR 22% and

median duration of response 21.7 weeks (range, 6.1-37.1 weeks) for other B-cell lymphomas.¹⁵ Similarly, brentuximab vedotin is active against CD30-positive cutaneous T-cell lymphomas and lymphoproliferative disorders: ORRs 50% and 100% for Mycosis Fungoides and primary cutaneous ALCL/lymphomatoid papulosis, respectively.¹⁶ However, it is unknown whether single-agent brentuximab vedotin is active against EBV- and CD30-positive lymphomas. Brentuximab vedotin monotherapy has previously been shown to be reasonably well tolerated in a phase 1 study and a phase 2 pivotal trial at 1.8 mg/kg in every 3 week dosing. Therefore, brentuximab vedotin at 1.8 mg/kg in every 3 week will be delivered in this study.

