4.2 Number of Patients

Based on the optimal Simon's two-stage design, at least 3 responders among stage 1 patients (N=10) are required to enter into a stage 2. The stage 2 will be delayed until the completion of ≥ 4 cycles of study medication in the last patient in stage 1, so-called interim analysis of stage 1. A total of 25 patients with EBV- and CD30-positive lymphomas will be enrolled.

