5.2 Exclusion Criteria

Patients meeting any of the following exclusion criteria are not to be enrolled in the study.

1. Female patient who are both lactating and breast-feeding or have a positive serum pregnancy test during the screening period or a positive pregnancy test on Day 1 before first dose of study drug
2. Any serious medical or psychiatric illness that could, in the investigator's opinion, potentially interfere with the completion of treatment according to the protocol.
3. Known cerebral or meningeal disease (EBV- and CD30-positive lymphoma or any other etiology), including signs or symptoms of PML
4. Symptomatic neurologic disease compromising normal activities of daily living or requiring medications
5. Any sensory or motor peripheral neuropathy greater than or equal to Grade 2
6. Known history of any of the following cardiovascular conditions
 - a. Myocardial infarction within 1 year of study enrollment
 - b. New York Heart Association (NYHA) Class III or IV heart failure (see Appendix 12.2)
 - c. Evidence of current uncontrolled cardiovascular conditions, including cardiac arrhythmias, congestive heart failure (CHF), angina, or electrocardiographic evidence of acute ischemia or active conduction system abnormalities
 - d. Recent evidence (within 6 months before first dose of study drug) of a left-ventricular ejection fraction <50%
7. Any active systemic viral, bacterial, or fungal infection requiring systemic antibiotics within 2 weeks prior to first study drug dose
8. Patients that have not completed any prior treatment chemotherapy and/or other investigational agents within at least 5 half-lives of last dose of that prior treatment
9. Known hypersensitivity to recombinant proteins, murine proteins, or to any excipient contained in the drug formulation of brentuximab vedotin.
10. Known human immunodeficiency virus (HIV) positive
11. Known hepatitis B surface antigen-positive, or known or suspected active hepatitis C infection
12. Diagnosed or treated for another malignancy within 3 years before the first dose or previously diagnosed with another malignancy and have evidence of residual disease. Patients with nonmelanoma skin cancer or carcinoma in situ of any type are not excluded if they have undergone complete resection.

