6 STUDY DRUG

6.1 Brentuximab Vedotin Administration

Study drug will be administered only to eligible patients under the supervision of the investigator or identified subinvestigator(s).

Brentuximab vedotin must not be administered as an IV push or bolus. Study treatment will be administered by IV infusion given over approximately 30 minutes on Day 1 of each 21-day cycle. In the absence of infusion toxicities, the infusion rate for all patients must be calculated in order to achieve a 30-minute (approximate) infusion period. Brentuximab vedotin will be administered through a dedicated IV line and cannot be mixed with other medications.

The dose of brentuximab vedotin is 1.8 mg/kg. Dosing is based on patients' weight according to the institutional standard; however, doses will be adjusted for patients who experience a $\geq 10\%$ change in weight from baseline. Actual weight will be used except for patients weighing greater than 100 kg; dose will be calculated based on 100 kg for these individuals. The dose will be rounded to the nearest whole number of milligrams.

Infusion-related reactions may occur during the infusion of brentuximab vedotin. The infusion should be administered at a site properly equipped and staffed to manage anaphylaxis should it occur. The patient should be observed for 60 minutes following the first infusion of brentuximab vedotin.

During this observation period, the IV line should remain open for at least 1 hour to allow administration of IV drugs if necessary. All supportive measures consistent with optimal patient care will be given throughout the study according to institutional standards. Medications for infusion-related reactions, such as epinephrine, antihistamines, and corticosteroids, should be available for immediate use.

Patients who experience a Grade 1 or Grade 2 infusion-related reaction may receive subsequent brentuximab infusions with premedication consisting of acetaminophen (650 mg orally) and diphenhydramine (25–50 mg orally or 10–25 mg IV) or according to institutional standards, administered 30 to 60 minutes prior to each 30-minute brentuximab vedotin infusion. The routine use of steroids as premedication is discouraged.

If a Grade 3 or greater infusion-related reaction consistent with anaphylaxis occurs, immediately and permanently discontinue administration of brentuximab vedotin and administer appropriate medical therapy as per institutional guidelines.

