7.1.1 Determination of Sample Size

Optimal Simon's two-stage design

- $\alpha=0.05$, $\beta=0.20$
- $P_0=0.20$, $P_1=0.45$
- Stage 1: 2/10 (≥ 3 responders are required to move to stage 2)
- Stage 2: 7/22 (8 or more responses are required to reject the null hypothesis)
- Total patients: $22 + 3$ (10% drop-out rate) = 25 patients

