7.1.3 Populations for Analyses

The populations used for analysis will include the following:

Safety population: patients who receive at least 1 dose of study drug will be used for all safety analyses. All patients in the safety population will be analyzed according to the actual treatment received.

Intent-to-Treat (ITT) population: all patients randomized to treatment. All patients in the ITT population will be analyzed according to the treatment they were randomized to receive and not according to what they actually received, if different.

Per-Protocol (PP) population: a subset of ITT patients who do not have a major protocol violation as determined by the project clinician. All decisions to exclude patients from the PP population will be made prior to database lock.

Response-Evaluable population: all patients with diagnosis as confirmed by an independent pathology review facility, with measurable disease at baseline, who receive at least 1 dose of study drug, and have at least 1 postbaseline response assessment.

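### Corticosteroids may be given as lymphoma treatment during this single-agent trial, and no analysis separates a response first seen after them from the primary ORR

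*Combined protocol and SAP*

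**What the plan says.** Section 1.5 gives the reason for the trial: "it is unknown whether single-agent brentuximab vedotin is active against EBV- and CD30-positive lymphomas". Section 4.1 describes an open-label, non-randomized study with ORR as its main measure.

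On concomitant treatment:

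- Section 6.4: "Corticosteroids are permitted as part of a chemotherapy premedication regimen or for the treatment of study disease per institutional standards". No dose, duration or timing limit is attached. The same bullet also allows topical steroids without limit.
- Section 6.3 opens with "The following medications and procedures are prohibited during the study" and then names only bleomycin.
- Section 6.1: "The routine use of steroids as premedication is discouraged". This concerns premedication only.
- Section 5.2, criterion 8, sets a washout for "any prior treatment chemotherapy and/or other investigational agents within at least 5 half-lives of last dose of that prior treatment". It does not name steroids still being taken at first dose.

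On the decisions, section 4.2 says "at least 3 responders among stage 1 patients (N=10) are required to enter into a stage 2", and section 7.1.1 says "8 or more responses are required to reject the null hypothesis", out of 22.

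On analysis, section 7.1.6 takes ORR from the revised lymphoma criteria or mSWAT, in the ITT population. The Per-Protocol population in section 7.1.3 is "a subset of ITT patients who do not have a major protocol violation as determined by the project clinician". Concomitant medications are recorded from consent to 30 days after the last dose (Schedule of Events) and coded to a drug dictionary (section 7.1.8).

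**The concern.** The protocol itself treats a corticosteroid as part of lymphoma therapy: section 1.5 lists prednisolone as a component of CHOP. Allowing steroids for the study disease therefore allows a second anti-lymphoma treatment alongside the drug under test. There is no control arm in which the same steroid effect would appear and cancel.

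Both decisions turn on single responses. A result of 8/22 (36.4%) rejects the null hypothesis and 7/22 (31.8%) does not. If one of eight responses first appeared after steroids given for the lymphoma, a reader could not tell from the planned output whether brentuximab vedotin alone would have reached the boundary. A separation made afterwards, in an open-label trial with responses already known, would carry little weight.

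The exposure is greatest for steroids started before the first on-treatment scan, which follows cycle 2, or during stable disease.

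**Working it through.** **Step 1. Does any section close the gap?**

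- Section 6.3 prohibits bleomycin only.
- Section 6.1 reaches routine premedication, not treatment of the lymphoma.
- Section 5.2, criterion 8, reaches chemotherapy and investigational agents before entry.
- Section 7.1.6 has one rule on other therapy. It is the third PFS event, for confirmed non-complete responders who get chemotherapy or radiotherapy after brentuximab vedotin is finished. It does not touch ORR and does not name steroids.
- Appendices 12.3 and 12.4 define response by lesion size, PET, marrow and skin score, whatever caused the change.
- The Per-Protocol set removes major violations. Use that section 6.4 permits is not in itself a violation.

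None of these separates the responses in question.

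**Step 2. Reproduce the design.** Inputs from section 7.1.1: P0 = 0.20, P1 = 0.45, 3 or more of 10 to continue, 8 or more of 22 to reject. The chance of rejecting at response rate p is

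R(p) = Σ (x = 3 to 10) P[Bin(10, p) = x] × P[Bin(12, p) ≥ 8 − x].

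At p = 0.20 the terms are:

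| x | P[Bin(10, 0.20) = x] | P[Bin(12, 0.20) ≥ 8 − x] | product |
|---|---|---|---|
| 3 | 0.2013 | 0.0726 | 0.0146 |
| 4 | 0.0881 | 0.2054 | 0.0181 |
| 5 | 0.0264 | 0.4417 | 0.0117 |
| 6 | 0.0055 | 0.7251 | 0.0040 |
| 7 to 10 | – | – | 0.0008 |

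R(0.20) = 0.0492 and R(0.45) = 0.8065. A full search for the optimal Simon design returns the same 2/10 and 7/22, so the plan's design is correct as stated.

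**Step 3. One patient certain to count as a responder; all others respond at 0.20.**

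- In stage 1: Σ (x = 2 to 9) P[Bin(9) = x] × P[Bin(12) ≥ 7 − x] = 0.1021. The chance of passing the gate rises from P[Bin(10) ≥ 3] = 0.322 to P[Bin(9) ≥ 2] = 0.564.
- In stage 2: Σ (x = 3 to 10) P[Bin(10) = x] × P[Bin(11) ≥ 7 − x] = 0.0899.

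These compare with 0.0492 when that patient responds at 20% like the rest. If the patient is known in advance to be a non-responder to the drug, the rates with conversion are still 0.1021 and 0.0899, but the baselines are lower, at 0.036 (stage 1) and 0.039 (stage 2).

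**Step 4. Assumed use and conversion.** The documents give neither. If a share f of patients who do not respond to the drug receive steroids and a share c of those become responders, the observed rate is 0.20 + 0.80 × f × c.

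| f | c | observed rate | false-positive rate |
|---|---|---|---|
| 0.05 | 0.20 | 0.208 | 0.060 |
| 0.10 | 0.20 | 0.216 | 0.073 |
| 0.20 | 0.20 | 0.232 | 0.102 |

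**Step 5. Cost of a ban instead.** As a worst case, suppose a share s of patients leave before responding and would have responded at 45%. Power is then R(0.45 × (1 − s)), and the chance of wrongly stopping at stage 1 is P[Bin(10, 0.45 × (1 − s)) ≤ 2].

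| s | power | wrongful stage 1 stop |
|---|---|---|
| 0 | 0.81 | 10.0% |
| 5% | 0.75 | 12.7% |
| 10% | 0.68 | 15.9% |

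**The case against.** Several objections have force.

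- **Rarity and template text.** The sentence speaks of chemotherapy premedication in a monotherapy trial, and section 6.1 discourages routine steroid premedication, so it may have been carried over from elsewhere. That is plausible, but the sentence governs as written.
- **Low conversion.** Patients must have failed one to four regimens including anthracycline-based chemotherapy, with exceptions for some subtypes. The protocol's own example, CHOP, contains prednisolone, so many patients may already have failed a steroid-containing regimen. A PR also needs a 50% fall in SPD. This argues for low conversion rates, and nothing in the documents supports high ones.
- **A legitimate estimand.** Counting every on-treatment response whatever else was given is defensible. This stands, and it is why the primary count should stay as it is.
- **Data already collected.** Concomitant medications are recorded and coded, so most of what a sensitivity analysis needs may exist. What is missing is the prespecified analysis and, possibly, the indication for each course; the case report form is not in the documents.
- **A ban may cost more than the problem.** At 10% use and 20% conversion the false-positive rate rises by 2.3 points. If 10% of patients left under a ban, worst-case power would fall by 12.7 points (0.8065 − 0.6793 = 0.127). This also stands.

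A reader might infer that deleting the phrase in section 6.4 would settle the matter. It would not: section 6.3 would still prohibit only bleomycin, withdrawal under section 6.12 is at the investigator's discretion, and section 7.1.6 would count the response as before.

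**Conclusion.** The gap is real and rests on what the plan states. Section 6.4 permits lymphoma-directed steroids, and nothing keeps a response first documented after them out of the primary ORR, the 3-of-10 gate or the 8-of-22 boundary.

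Its size is conditional. One certain responder takes the false-positive rate from 4.9% to 9.0% or 10.2%; assumed use of 10% with 20% conversion takes it to 7.3%. These are illustrations on the 22-patient design with independent patients and a true rate of 20%. They are not forecasts.

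A reader might go further and conclude that the ORR will be materially inflated or that the trial's error rate is not controlled. The documents do not support that: they give no rate of steroid use and no steroid response rate, and use may be rare. Severity is minor.

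**What to change.** **Main change.** Keep all responses in the primary ORR and in the stage 1 decision. Prespecify in section 7.1.6 a sensitivity analysis, also shown at the stage 1 review, that counts as non-response any CR or PR first documented after:

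- systemic steroids given for the lymphoma; or
- topical steroids applied to scored lesions, in patients assessed by mSWAT.

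Capture the indication and dates of each steroid course, including courses ongoing at first dose. List all systemic courses whatever their stated indication, so that one labelled symptom control can be seen.

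*Cost:* one extra analysis, perhaps one or two form fields, and a supporting figure that may be less favourable. Sample size, boundaries and planned power (0.81) do not change.

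**Optional, if the permission was not intended.** Remove the study-disease clause from section 6.4, and also add systemic steroids given as lymphoma treatment to the prohibited list in section 6.3 while patients are on study drug. Premedication and infusion-reaction use stay allowed. Both edits are needed. *Cost:* patients who need steroids for the lymphoma may leave study treatment, with worst-case power of 0.75 or 0.68 if 5% or 10% leave before responding.

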6.5 Precautions and Restrictions

Infusion-Related Reactions

All infusions should be administered at a site properly equipped and staffed for anaphylaxis should it occur. Medications for treatment of hypersensitivity reactions, such as epinephrine, antihistamines and steroids, should be available for immediate use in the event of a reaction during administration and also during the observation period following the first brentuximab vedotin infusion.

Pregnancy

It is not known what effects brentuximab vedotin has on human pregnancy or development of the embryo or fetus. Therefore, female patients participating in this study should avoid becoming pregnant, and male patients should avoid impregnating a female partner. Non-sterilized female patients of reproductive age group and male patients should use effective methods of contraception through defined periods during and after study treatment as specified below:

Female patients must meet 1 of the following:

- Postmenopausal for at least 1 year before the screening visit, or
- Surgically sterile, or
- If they are of childbearing potential, agree to practice 2 effective methods of contraception from the time of signing the informed consent form through 6 months after the last dose of study drug, or agree to completely abstain from heterosexual intercourse.

Male patients, even if surgically sterilized (i.e., status post-vasectomy) must agree to one of the following:

- Practice effective barrier contraception during the entire study treatment period and through 6 months after the last dose of study drug, or completely abstain from heterosexual intercourse.

6.6 Management of Clinical Events

Peripheral Neuropathy

Collectively, the data support that peripheral neuropathy is an effect of cumulative exposure to brentuximab vedotin. The first onset of any grade peripheral neuropathy increased incrementally with increasing numbers of cycles, and a trend toward increased incidence of first onset of Grade 3 peripheral neuropathy and peripheral motor neuropathy in later cycles was apparent. In line with these observations, the incidences of peripheral neuropathy (any SMQ event, Grade 3 event, and/or motor event) were highest in later cycles.

Neuropathy associated with brentuximab vedotin was managed using a combination of dose delay and reduction to 1.2 mg/kg. Dose delay and reduction appeared to mitigate worsening of neuropathy. For new or worsening Grade 2 or 3 neuropathy, dosing should be held until neuropathy improves to Grade 1 or baseline and then restarted at the 1.2 mg/kg dose level (or as specified in individual protocols). For Grade 4 peripheral neuropathy, brentuximab vedotin should be discontinued.

Hematological Toxicities

The hematological AEs of thrombocytopenia, anemia, and neutropenia were reported in the pivotal studies. Neutropenia was the most common hematological AE (21%) and was not unexpected based on the toxicology results from the sponsor's nonclinical program and phase 1 safety and clinical pharmacology studies. Although neutropenia was a common treatment-emergent AE in the pivotal studies, it appeared to be well managed with the protocol-specified recommendations for hematologic toxicity (i.e., dose delay, growth factor support). The median duration of Grade 3 or Grade 4 neutropenia was limited (1 week); 3 patients had Grade 4 neutropenia that lasted ≥ 7 days. Less than half of the patients with Grade 3 or 4 neutropenia had temporally associated infections, and the majority of temporally associated infections were Grade 1 or 2. Although not reported in the pivotal studies, febrile neutropenia has been reported in additional completed studies with brentuximab vedotin. Patients should be monitored for cytopenias.

For new or worsening Grade 3 or 4 neutropenia, dosing should be held until neutropenia improves to \leq Grade 2 or baseline and then restarted at the same dose level (or as specified in individual protocols). Growth factor support (G-CSF or GM-CSF) should be considered for subsequent cycles (refer to Dose Modification Section 6.2).

Infusion-Related Reactions

Brentuximab vedotin is administered via IV infusion. Infusion of proteins can result in hypersensitivity reactions that may be fatal if not rapidly and appropriately managed. Infusion

interruption for IRR treatment generally led to the successful completion of the dose and continued treatment with brentuximab vedotin with or without IRR prophylaxis, according to the clinical judgment of the investigator.

Although the experience with IRRs related to brentuximab vedotin is limited, in part due to the low incidence observed to date, data support brentuximab vedotin administration by appropriately trained personnel without the need for routine prophylaxis. If IRR symptoms develop, the infusion should be interrupted and appropriate medical management instituted. The infusion may be restarted at a slower rate after symptom resolution. Premedication should be administered for subsequent infusions in patients who have experienced a prior IRR. If anaphylaxis occurs, brentuximab vedotin should be immediately and permanently discontinued and appropriate medical management instituted.

Infections

Serious and opportunistic infections have been reported for patients treated with brentuximab vedotin. Monitor patients for the emergence of possible bacterial, fungal, or viral infections.

Although infections were observed in 61% of patients in the completed phase 2 studies (Studies SG035-0003 and SG035-0004), the majority of infections were Grade 1 to 2 and occurred with an incidence comparable to that reported in similar populations. While serious infections were reported in 10% of patients, the majority of infections were not considered by the investigator to be related to brentuximab vedotin. Infection led to dose delay in 14% of HL patients and 7% of ALCL patients. No patient discontinued treatment because of infection. The infection with the highest incidence was Grade 1 or 2 URTI, which occurred in more HL than ALCL patients. Grade 3 or 4 infections occurred in 7% of HL patients and 12% of ALCL patients. No Grade 5 infections were reported. HL patients had a higher incidence of infections, largely reflective of the higher incidence of Grade 1 to 2 URTI (37%). Several factors may have contributed to this higher incidence, including the high frequency of respiratory tract infections in HL patients post-transplant, the lower median age of the HL patients compared with systemic ALCL patients, and differences in exposure to respiratory viruses. These URTIs, while frequent, led to dose delay in only 3 patients. Importantly, the rate of pneumonia was low, which is indicative of a low rate of progression from URTI to pneumonia, and the incidence was lower than that reported in the literature for comparable populations.

Stevens-Johnson Syndrome

Stevens-Johnson syndrome and toxic epidermal necrolysis have been reported with brentuximab vedotin. Fatal outcomes have been reported. If Stevens-Johnson syndrome or toxic epidermal necrolysis occur, brentuximab vedotin must be discontinued and the appropriate medical therapy administered.

Tumor Lysis Syndrome

Tumor lysis syndrome (TLS) is typically reported in patients with acute leukemias and high-grade non-Hodgkin lymphomas after the initiation of cytotoxic therapy.

TLS has been reported with brentuximab vedotin. Patients with rapidly proliferating tumor and high tumor burden are at risk of tumor lysis syndrome. These patients should be monitored closely and managed according to best medical practice. Management of TLS may include aggressive hydration, monitoring of renal function, correction of electrolyte abnormalities, anti-hyperuricaemic therapy, and supportive care.

Progressive Multifocal Leukoencephalopathy

PML can occur in patients receiving brentuximab vedotin. PML is a rare demyelinating disease of the brain that is caused by the John Cunningham virus (JCV). It typically occurs in immunocompromised individuals and can be fatal. Presenting features may include altered mental status, motor deficits such as hemiparesis or ataxia, visual disturbances, or higher cortical dysfunction such as dysphasia or agnosia. Seizures have also been reported in PML patients (approximately 20%). The onset of neurological deficits may occur over weeks to months.

Cognitive decline without accompanying deficits in motor or sensory function is uncommon. Optic nerve involvement, fever, and spinal cord disease are not typically associated with PML. In addition, peripheral neuropathy, which has been reported with brentuximab vedotin treatment, is not commonly reported with PML.

If PML is suspected, a diagnostic work-up should be performed. The work-up may include, but is not limited to:

- Neurologic examinations, as warranted
- Brain MRI: features suggestive of PML include presence of unifocal or multifocal lesions, mainly of the white matter, which are typically non-enhancing and do not have mass effect.
- PCR analysis: JCV DNA detectable in CSF or there is evidence of JCV in a brain biopsy
- Neurology consultation

Brentuximab vedotin dosing should be held if PML is suspected. If PML is confirmed, brentuximab vedotin should be permanently discontinued.

Pulmonary Toxicity in Combination with Bleomycin

Concomitant use of brentuximab vedotin and bleomycin is contraindicated due to pulmonary toxicity. In a clinical trial that studied brentuximab vedotin with bleomycin as part of a combination regimen (ABVD), the rate of noninfectious pulmonary toxicity was higher than the

historical incidence reported with ABVD. Monotherapy with brentuximab vedotin has not been associated with a clinically meaningful risk of pulmonary toxicity. In the event of new or worsening pulmonary symptoms (e.g., cough, dyspnoea), a prompt diagnostic evaluation should be performed and patients should be treated appropriately.

Acute Pancreatitis

Acute pancreatitis has been reported for patients treated with brentuximab vedotin. Patients should be monitored for signs of new or worsening acute abdominal pain and, if observed, a diagnostic workup for pancreatitis should be considered. A diagnostic workup may include physical examination, laboratory evaluation for serum amylase and serum lipase, and abdominal imaging, such as ultrasound and other appropriate diagnostic measures. Brentuximab vedotin should be held for any suspected case of acute pancreatitis. Brentuximab vedotin should be discontinued if a diagnosis of acute pancreatitis is confirmed.

Hepatotoxicity

Hepatotoxicity, predominately in the form of asymptomatic mild to moderate transient elevations in AST and/or ALT, has been reported for patients treated with brentuximab vedotin. Patients should be monitored for elevated liver enzymes.

Embryogenesis, Reproduction, and Spermatogenesis

The effects of brentuximab vedotin on embryogenesis, reproduction, and spermatogenesis in humans are unknown. In addition, data about the effects of brentuximab vedotin in pregnant women are unavailable. Therefore, women of childbearing potential and fertile men should be advised to use adequate and effective contraception during and after treatment with brentuximab vedotin.

